The fundamental mechanism of action for rTMS is modulation of brain excitability. 15 rTMS at frequencies of 5-Hz and higher has been found to transiently enhance the excitability, 16 whereas rTMS at frequencies of 1-Hz and lower has been found to depress the cortical excitability. 17 Many rTMS studies have also shown that repeated sessions of rTMS therapy results in cumulative persistent benefits that can last several weeks. For example, in a recent double blind randomized controlled study, low frequency rTMS delivered over eight weeks to Parkinson's disease patients showed positive clinical benefits that lasted 12 weeks beyond the last rTMS session. 18 In this proposal we plan to employ a two week course of rTMS therapy to achieve sustained benefits. With standard BoNT treatment, the peak-dose benefits are seen at about 4-6 weeks after the administration of injections. We plan to introduce rTMS during this peak-dose period (about 6 weeks after BoNT or T1). We will examine the effects of combined therapy at about 10 weeks after BoNT injections (T2) and at about 12 weeks after BoNT injections (T3). We will also measure the physiological effects at these time points. We will use the blink reflex recovery (BRR) curve that reflects the brain stem excitability. An increased BRR indicates that there is increased excitability of facial motor neurons and bulbar interneurons. BRR has been shown to be increased in a significant proportion of patients with BEB. 19,20 According to the animal model of blepharospasm, one of the underlying mechanisms for increased BRR is that a loss of dopamine-containing neurons in the substantia nigra pars compacta causes a decreased inhibition in the blink circuit.²¹

In summary, BEB is a functionally disabling focal dystonia. BoNT therapy is suboptimal in many BEB patients. rTMS therapy is a promising noninvasive therapy and has shown positive benefits in BEB. rTMS therapy can be Protocol Version 08/10/2015

easily combined with BoNT injections to enhance the effects of BoNT in BEB. We plan to collect pilot data on this novel approach in this one year application. The specific aims for the proposal are:

[figure not shown]
Aim 1: Clinical impact of rTMS therapy in BEB.

[figure not shown]

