We will determine the clinical effects of 0.2 Hz rTMS therapy of the ACC when combined with BoNT injections in BEB. Comparisons will be drawn between the T1, T2 (about 10 weeks after BoNT) and T3 (about 12 weeks after BoNT) assessments in the clinical scoring of BEB symptoms and patient rating of quality of life. We hypothesize that in comparison to T1 assessment; there will be an increased control of BEB symptoms and patient rating of quality of life at T2 follow-up. These benefits will remain sustained at T3 follow-up though to a lesser extent.

Aim 2: Physiological impact of rTMS therapy in BEB

Aim 2a: We will determine the physiological effects of 0.2 Hz rTMS therapy of the ACC when combined with BoNT injections in BEB. We will record the time course of effects on BRR at T1, T2 and T3 assessments. We hypothesize that in comparison to T1 assessment, BRR will be reduced and reach physiological levels at T2 follow-up. BRR will continue to remain at physiological levels at T3 follow-up though to a lesser extent than at T2.

Aim 2b: We will determine if the effects of 0.2 Hz rTMS therapy on BRR will correlate with clinical scoring of BEB symptoms. We hypothesize that the change in BRR at T2 and T3 will show positive correlation with the improvement in BEB symptoms at these time points.

rTMS will be delivered over the ACC with a figure-of-eight coil.

Figure 1:
A shows the schedule for rTMS intervention and monitoring of clinical and physiological outcomes
B shows the target in the brain for rTMS intervention

METHODS

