SAMPLE SIZE, EXPECTED OUTCOME AND STATISTICAL ANALYSIS: With an expected difference of 30% in the primary outcome measure¹⁴ between before (T0) and after rTMS therapy (T1), a standard deviation of 20%, type I error of 5% and power of 80%, the necessary sample size for each group has been determined. In this one year pilot study we propose to enroll a total of 16 BEB subjects with eight subjects in each treatment arm and 16 healthy controls for normative physiological data. Descriptive statistics will be used for the demographic data. Data will be presented as mean (SD) unless otherwise indicated. We will examine each of the dependent measure separately. These include the eye blink rate, number of sustained blinks, the time of eye closure, patient rating of blepharospasm and the BRR cycle. For Aim 1 and Aim2a, each dependent measure will be examined using the following statistical approach. We will conduct a mixed model analysis using time and stimulation arm as repeated factors adjusted for baseline values, and subjects as the random factor. The model will include 2 within-subject factors: treatment (2 levels: active vs sham) and time (3 levels: T1, T1, and T3). If the interaction effects between stimulation arm and time are found as non-significant, they will be dropped. In case of significant main effects, post hoc pairwise comparisons will be corrected using Fisher least significant difference procedure in accordance with the closed test principle; i.e., post hoc comparisons will be declared non-significant if the global p value of the main effect (testing equality of all 2 stimulation arms simultaneously) are non-significant, but will be carried out without further correction in case of a significant global main effect. SPSS version 15.0 for Windows will be used for statistical computations. The 2-tailed significance level will be set at 0.05. For Aim 2b, we will use Spearman correlation test to determine the relation between the change in BRR and change in clinical scores at T2 compared to T1 and at T3 compared to T1.

POTENTIAL PROBLEMS

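### T1 is labelled both before and after rTMS; if it is pre-rTMS, keeping it as an outcome level dilutes the arm effect

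*Combined protocol and SAP*

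**What the plan says.** All places are in the combined protocol and SAP.

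- **Sample size section, first sentence:** the 30% difference is the one expected "between before (T0) and after rTMS therapy (T1". Here T1 follows rTMS.
- **Background:** "We plan to introduce rTMS during this peak-dose period (about 6 weeks after BoNT or T1". Here T1 is about week 6, when rTMS begins. Methods also starts rTMS at about six weeks, and the rTMS therapy section runs it daily over 10 days.
- **Aim 1:** the hypothesis for T2 (about week 10) is that "in comparison to T1 assessment; there will be an increased control of BEB symptoms". For T3 (about week 12): "These benefits will remain sustained at T3 follow-up though to a lesser extent". Aim 2a uses T1 in the same way.
- **Aim 2b analysis:** correlations use the "change in clinical scores at T2 compared to T1 and at T3 compared to T1".
- **Model:** a mixed model "using time and stimulation arm as repeated factors adjusted for baseline values", with subject as random factor and "time (3 levels: T1, T1, and T3". The baseline visit is not named.
- **Interaction rule:** "If the interaction effects between stimulation arm and time are found as non-significant, they will be dropped".
- **Post hoc rule:** pairwise comparisons count as non-significant unless the global main effect across the two arms is significant.

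Figure 1A, the schedule, is not available in the text and may define T0.

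**The concern.** T1 cannot be both the visit after rTMS and the week-6 reference visit at which rTMS begins. The time-level list does not settle it, since it prints T1 twice and omits T2 (probably a misprint for T1, T2, T3).

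Suppose T1 is pre-rTMS. Randomised arms then differ at T1 only by chance, and the rTMS effect lies in how the arms separate at T2 and T3. A main effect of arm averaged over T1, T2 and T3 includes a visit at which the true effect is zero. That comes from treating T1 as an outcome, and it holds even if the interaction stays in the model. Dropping a non-significant interaction makes it worse, because the averaged coefficient is then the only arm effect that the model reports. The post hoc rule also makes the visit comparisons depend on the averaged test.

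The study exists to collect pilot data, so the effect estimate is one of its main products. A diluted estimate, used alone, could mislead the planning of a later trial.

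**Working it through.** **The plan's own figure.** Inputs from the sample size section: difference 30, SD 20, two-sided 5%, power 80%.
- Normal approximation: 2 × (1.960 + 0.842)² × 20² / 30² = 6.98, so 7 per arm.
- Exact two-sample t test at 8 per arm: power 79.7%.

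The planned 8 per arm is reproduced.

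**Size of the dilution.** Let d1, d2, d3 be the active-minus-sham differences at T1, T2, T3. With complete data, a random subject intercept and equal visit weights, the arm coefficient of the additive model is (d1 + d2 + d3)/3. A mixed-model fit to one simulated data set confirmed this: visit differences 5.37, 36.12 and 30.37 have mean 23.95, and the fitted arm coefficient was 23.95. If T1 is pre-rTMS, d1 = 0 in expectation. The documents give no T3 figure, so the T3 effects below are assumed, and the 30 points are placed at T2.

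| T2 / T3 effect | Arm estimate, T1 kept | T2-T3 mean |
|---|---|---|
| 30 / 30 | 60/3 = 20.0 | 30.0 |
| 30 / 20 | 50/3 = 16.7 | 25.0 |
| 30 / 15 | 45/3 = 15.0 | 22.5 |

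The ratio is 2/3 in each row.

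**How often the interaction is dropped.** Assumptions: 8 per arm, SD 20 at every visit, compound symmetry, correlation r = 0.3, 0.5 or 0.7. The test is F on 2 and 28 df (critical value 3.34). Its noncentrality is 4 × S / (400 × (1 − r)), where S is the sum of squared visit effects about their mean.
- 30/20: effects 0, 30, 20 have mean 16.67, so S = 277.8 + 177.8 + 11.1 = 466.7. Noncentrality is 6.67, 9.33, 15.56, and the term is dropped in 42/26/7% of trials.
- 20/10: S = 100 + 100 + 0 = 200. Noncentrality is 2.86, 4.00, 6.67, and it is dropped in 72/62/42%.
- 30/30: S = 600, and it is dropped in 30/16/3%.

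**Power of the arm test, effects 30/20.** Simulation with 20,000 trials per correlation, least squares on subject means with one covariate (13 residual df):

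| Baseline covariate | T1 kept as outcome | T2 and T3 only |
|---|---|---|
| Separate T0 | about 60/64/76% | 84/88/96% |
| T1 | about 84/88/96% | about 84/88/96% |

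The second row is an identity. The three-visit mean equals T1/3 + (2/3) × (T2-T3 mean). With T1 as covariate, the T1/3 part is absorbed, so estimate and standard error both shrink by a third and the t statistic does not change. In the simulations the two t statistics agreed to rounding error in every trial.

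**The case against.** The strongest reply is that the dilution rests on two inferences: that T1 is pre-rTMS, and that T1 is meant to be an outcome level. The only level list is garbled, the only before/after definition in the same section puts T1 after rTMS, and Figure 1A might settle the matter. This stands as a condition on the result. It does not remove the conflict between the sample size section and the Background and Aims.

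A reader might infer four stronger things that the documents do not support.
- **That the interaction rule alone causes the bias.** Averaging over T1 dilutes the main effect even with the interaction kept.
- **That the estimate is always two thirds.** The plan states no residual covariance. Without a baseline covariate, AR(1) with correlation 0.5 to 0.7 gives about 0.50 to 0.60, and examples with unequal visit variances run from 0 to 0.88. If the outcome is percentage change from T1, T1 is zero for everyone and equal variances fail; 0.667 then holds only for an equal-weight fit.
- **That power is lost in any case.** It is lost only if a separate T0 is the covariate.
- **That dropping the interaction is always, or never, the usual outcome.** It is a minority event for the 30-point patterns, but occurs in up to 72% of trials for 20/10.

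It is also fair that this is a one-year pilot with results presented as mean (SD), so visit-level differences may still be visible. That limits the harm but does not give the model a defined estimand.

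**Conclusion.** The concern holds in conditional form and should be fixed. The contradictory T1 labels, the faulty level list and the unnamed baseline are certain from the text. If T1 is pre-rTMS, which most of the text indicates, the averaged arm effect is diluted: by one third under complete data and equal visit weights, and by a different fraction under other covariance structures. Relative to T2 alone the shortfall is larger if T3 is smaller, as Aim 1 expects: 16.7 against 30 in the 30/20 case.

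The cost in power depends on the unnamed baseline: about 24/24/20 percentage points at correlations 0.3/0.5/0.7 with a separate T0 covariate, and none with T1 as covariate. These figures rest on SD 20 at every visit and on assumed correlations and T3 effects; the documents supply only the 30% difference and the 20% SD. If T1 is after rTMS, the dilution does not arise, but T1 is then not a pre-treatment reference for T2 and T3.

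**What to change.** 1. Define T0 to T3 against the start and end of the rTMS course, and reconcile the Background, the Aims and the sample size section with that definition. Correct the list of time levels.
2. Name the last pre-rTMS value as the baseline covariate and use only post-rTMS visits as outcomes. If the last pre-rTMS visit is T1, it serves only as the covariate, and T2 and T3 are the outcomes.
3. Keep arm-by-time in the model whatever its p-value.
4. Pre-specify the active-minus-sham contrasts at T2 and T3, either in a stated order or as their mean (the sponsor's choice), and do not gate them on a main effect that includes T1.

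The cost is analysis wording only, with no new visits or data. Keeping arm-by-time over two visits uses one degree of freedom.
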